## 6. STUDY DESIGN

### 6.1 General study design and justification of design

This is a controlled, randomized, open label, comparative clinical investigation conducted monocentric at the premises of Bernafon in Bern, Switzerland.

The exploratory study is based on a population of hearing impaired people that have hearing loss appropriate for the IMD.

As an RMD the subjects' current hearing instruments (Bernafon device) will be used. Additionally, a control situation may be when an unaided test condition is used or a test condition with a feature on or off.

There is no placebo or "fake" device that does not provide amplification. A single group assignment design is used with test subjects that have worn the RMD for at least 6 months and will now be fit with the IMD. Most of the testing will be unblinded as the subjects are familiar with the RMD which will be used as the control. They will recognize when they are using a different device. In situations where one device is used but programmed with two different programs the test subjects will be blinded. They will not be told the difference between the two programs. They will, for example, have a feature on in one and off in another.

A randomized test order will be used to test in a simulated environment. The test subject will be tested using unaided and aided conditions in a randomized manner for speech testing, listening effort, and subjective evaluations of sound and benefit perception. Or as stated above, the testing may be single-blinded by using only the IMD and programming different states into the device for comparison testing in which the test subject will not be aware of the differences.

The participants will be expected to participate for approximately 4 months for a combinations of field tests and lab tests. For lab tests they will not spend more than 2 hours in the clinic for testing, but will be expected to come for 5-6 sessions. Field trial periods will not last more than 14 +/-3 days.

The sequence will begin with the preparation phase in which participants are invited to the clinic for testing to determine if they are candidates for the trial. The entire test procedure will be explained, and they will be given a Patient Informed consent form read which will need to be signed, dated, and returned before any testing begins.

The following appointments will include a series of field tests with corresponding lab test appointments. There could be up to 6 appointments, but will not exceed 2 hours each time. During these appointments they will participate in speech testing, listening effort testing, perceived loudness testing, and subjective evaluations of sound and benefit of the hearing aids. Subjects will be given questionnaires and diaries to complete with all field test periods.

After they have completed all appointments the clients will receive instructions about the continued use of the RMD and the reminder that they are welcome to come to the clinic for any maintenance of the aids.

### 6.2 Methods of minimising bias

#### 6.2.1 Randomisation

For one period of the field tests the subjects will be divided into two groups. One group will begin the trial with the new feature [REDACTED] programmed in the IMD and the other group will have the feature turned off. They will be given two sets of IMDs (one with and one without the feature). They will be instructed to wear one pair of devices for the first 7 days and then to switch to the other pair of devices. After two weeks (+/-3d) of use they will return to the clinic for an appointment. The allocation to the groups will be randomized using stratification in order to maintain balance between the two test groups. The stratification will be based on degree of hearing loss and frequency lowering prescription (on/off). For lab tests the assignment to the test condition will also be randomized.

### **6.2.2 Blinding procedures**

The subjects will know that there are two programs (or two pairs of aids), but they will not know what the differences between them are. The program setting/device set up will be randomized so that not all test subjects have the same setting of [REDACTED] for program one and for program two. For example, program/device one may have [REDACTED] programmed for some subjects and for others program/device two will have [REDACTED] programmed. This will also help control any bias toward one program. The PI will be blinded concerning the two sets of devices. The statistician will create the randomization list and any pre-programming of devices needed to blind the PI.

### **6.2.3 Other methods of minimizing bias**

Validated questionnaire will be used to minimize bias. Diaries will be recorded by the subjects of their experience, and questions during interview sessions during the appointments will be created in a non-leading manner.

## **6.3 Unblinding Procedures (Code break)**

The statistician will maintain the documentation of blinding procedures. The [REDACTED] feature testing will be blinded and will be managed by the statistician. For all other testing the difference between the IMD and the RMD will be clear to the subjects due to the differences in hardware.

## 7. STUDY POPULATION

The study will take place in the clinic at Bernafon AG in Bern. There will be no other sites used for the testing.

### 7.1 Eligibility criteria

Participants fulfilling all of the following inclusion criteria are eligible for the study:

- All classifications of hearing loss (sensorineural, conductive, combined)
- If the hearing loss is conductive or combine it must be approved for amplification by a physician
- All shapes of hearing loss (flat, sloping, reverse slope, notch)
- Hearing loss severity ranging from mild to severe
- German speaking
- Both genders
- Ages 18 and older
- Ability and willingness to sign the consent form

The presence of any one of the following exclusion criteria will lead to exclusion of the participant:

- Contraindications for amplification
- Active ear disease
- Inability to follow the procedures of the study due to language problems, psychological disorders, dementia, or other cognitive problems of the participant,
- A reduced mobility making them unable to attend weekly study appointments
- A reduced ability to describe auditory impressions and the usage of the hearing aids
- Uncooperative so that it is not possible to record a valid pure tone audiogram
- A strongly reduced dexterity
- Central hearing disorders
- Bernafon employees
- Family members of Bernafon employees

### 7.2 Recruitment and screening

Bernafon has its own database of test subjects that come to Bernafon for updated fittings and general maintenance of their hearing aids. These test subjects do not consist of employees of Bernafon or family members of employees. The test subjects for the current study will be chosen from the internal subject database. Bernafon does not advertise as a method of recruiting participants. Participants are collected and added to the database by word of mouth. Current subjects will refer another person as a potential candidate to participate as a test subject. Additionally, if someone knows of another person with hearing loss they may give them the contact information of an audiologist within Bernafon. The person can then contact Bernafon if they wish to have a hearing test and determine if they're eligible to participate in a study. They first have a diagnostic audiological exam to determine if they have a hearing loss and the severity. If there are any medical indications it is recommended that they see a physician and then return if there are no contra-indications for hearing aids. During the hearing exam and medical history discussion it is determined whether the person is cognitively able to act on their own behalf. Additionally if the person comes alone or if they are accompanied will help to determine their level of independence. The potential study will be explained to the patients at this time and an approximate timeline will be outlined with an estimation of how much time/number of appointments would be required of them. It is explained that there is compensation of time by means of a box of batteries and cleaning accessories.

### 7.3 Assignment to study groups

For the field tests the allocation to the groups will be randomized using stratification in order to maintain balance between the two test groups. The stratification will be based upon the hearing loss of the participants, and more specifically the pure tone average and individual frequency lowering prescription (on/off). The idea is to avoid that any results are affected by one of these factors being more heavily represented in one group versus the other. For lab tests the assignment to the test condition will also be randomized. The test condition order will be randomized using a latin square design. This will minimize the bias created when one test condition is tested in the first or last position all of the time.

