Study Product / Intervention:	
[REDACTED]
 
The new investigational device will be the [REDACTED] hearing device. The products will have the same features (with the exception of one new) and processing. The differences will be the hardware style and processing chip. Hearing instruments are generally worn for approximately 10 hours every day and removed at night. The test clients will wear the new devices for a time period of 2-3 weeks for each field trial period. In between periods they will wear their current devices.
 
The tested medical devices will be in a stable stage of development. This means that system testing will be completed to ensure correct implementation and safe behavior of the devices before any testing on people is conducted. This also includes the software with which the devices are programmed. The software will be at a stable stage of development

Control Intervention (if applicable):	The reference devices are the subjects' current hearing instruments which are already CE marked, ie. previous technology Bernafon devices. The performance of the new devices will be measured against the previous technology.

Number of Participants with Rationale:	There will be an exploratory analysis of data only. The total number of participants will be approximately 35. For 90% power at the 0.05 significance level, the required sample size is about 24 subjects to detect non-inferiority of the current marketed device with an SD of 2 dB and non-inferiority $\delta$ of 1.3 dB.
Study Duration:	Approximately 4 months The screening of the participants will begin in February of 2017 and the final data collection appointments will occur in May 2017.
Study Schedule:	The first participant is expected to begin in February 2017. The last participant is expected to finish the testing in May 2017.
Investigator(s):	[REDACTED] [REDACTED] [REDACTED] [REDACTED]
Study Centre(s):	The testing will be performed at a single site in [REDACTED] at the [REDACTED].

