## 11.2 Determination of Sample Size

For non-inferiority testing, sample size calculations are the same as those for a 1-tailed test for superiority when the specified  $\delta$  is the same as the superiority population difference to detect (Masha & Sessler, 2011). The sample size calculation follows the recommendation from Chow & Wang (2008), where  $sd$  is the standard deviation,  $\alpha$  the significance level,  $1-\beta$  the power, and  $\delta$  the non-inferiority margin:

$$n = \frac{sd^2 \times (z_{1-\alpha} + z_{1-\beta})^2}{\delta^2}$$

For 90% power at the 0.025 significance level, the required sample size is about 24 subjects to detect non-inferiority of the marketed RMD with an SD of 2 dB and non-inferiority  $\delta$  of 1.3 dB. (Chow & Wang, 2008, p. 52).

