#### 11.4.2 Primary Analysis

Speech Reception Threshold (SRT) will be measured in a single lab test under three test conditions: unaided, control (RMD), and test (IMD) after appropriate training. Test condition order will be randomized using a Latin square design to control any potential order effect. The difference between control and test condition will be compared to the non-inferiority margin to test for non-inferiority. The unaided condition will be used as control of the investigational device benefit if non-inferiority could not be shown.

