3.1 Non-Inferiority margin determination

Non inferiority margin set with the following rationale (S. Kaul et al., 2005): "One proposal for selecting the margin is to take one-half of the magnitude of the worst limit of this Cl—the so-called "50% rule" or "95-95"

[figure not shown]

method" recommended by the FDA" with unaided condition instead of placebo.

Some considerations:

Assay sensitivity: "the ability to detect differences between treatments if such differences exist." Metaanalysis on effect size (see section 1.2) has shown that there is a positive effect of amplification with speech reception threshold measure (effect = 0.82, SE = 0.41, and p = 0.04).

Constancy assumption: "which assumes that the historical difference between the active control and placebo will be constant in the setting of the current active control trial if a placebo control had been used." Experimental factors like speech material, noise location, and hearing aid type has no significant influence on the amplification effect size. However, we think that the reference test (16REF) presents most similarities with the experimental test design. As the differences are very small regarding the overall effect, we will use the confidence interval of 16REF, for the computation of the non-inferiority margin.

n.i.m.<-2-reviewSummary\$ci.low[reviewSummary\$study=="16REF"]/2
round(n.i.m., 1)

[1] 1.3

The non-inferiority margin for the trial will be set to 1.3 dB.

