3.2 Non-inferiority test hypothesis

Lower SRT indicates a better performance, i.e. a positive difference like between unaided and aided shows an improvement with amplification. Following values definition: The current marketed device is the control: C,

The investigational device is the test: T,

The non-inferiority margin: M.

So if C-T < 0 then C is better than T and if C-T > 0 then T is better than C.

Test Hypothesis

Under H0: C - T <= - M, i.e. non-inferiority not found

Under H1: C - T > - M, i.e. T significantly non-inferior to C

Test analysis

[figure not shown]
The paired t-test usually tests that the mean differences are zero. The non-inferiority test compares the difference to a non-zero quantity -M.

The assumptions of the paired t-test are:

- 1. The data are continuous (not discrete).
- 2. The data, i.e., the differences for the matched-pairs, follow a normal probability distribution.
- 3. The sample of pairs is a simple random sample from its population. Each individual in the population has an equal probability of being selected in the sample.

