3.3 Switching to superiority hypothesis

If the confidence interval for the difference between both devices lies entirely above 0, then "it is acceptable to calculate the P value associated with a test of superiority and to evaluate whether this is sufficiently small to reject convincingly the hypothesis of no difference. There is no multiplicity argument that affects this interpretation because, in statistical terms, it corresponds to a simple closed test procedure. Usually this demonstration of a benefit is sufficient on its own, provided the safety profiles of the new agent and the comparator are similar."

Reference: Committee for Proprietary Medicinal Products (CPMP). (2001). Points to consider on switching between superiority and non-inferiority. British Journal of Clinical Pharmacology, 52(3), 223–228.

4. Required sample size

Reference: Chow S, Shao J, Wang H. 2008. Sample Size Calculations in Clinical Research. 2nd Ed. Chapman & Hall/CRC Biostatistics Series. page 52.

With the following requirements: non-inferiority margin: 1.34, standard deviation: 2 dB, alpha: 0.025, beta: 0.1.

Required sample size:

```
delta <- n.i.m.

sd <- reviewSummary$standev[reviewSummary$study=="16REF"]

alpha <- 0.025

beta <- 0.1
```

out.sample.size <- (sd*(qnorm(1-alpha)+qnorm(1-beta))/delta)^2 ceiling(out.sample.size)

[1] 24

A sample size of 24 will be use to test the non-inferiority hypothesis with a non-inferiority margin of 1.3 dB.

5.References

Alworth, L. N., Plyler, P. N., Reber, M. B., & Johnstone, P. M. (2010). The effects of receiver placement on probe microphone, performance, and subjective measures with open canal hearing instruments. Journal of the American Academy of Audiology, 21(2010), 249–266. http://doi.org/10.3766/jaaa.21.4.4

Committee for Proprietary Medicinal Products (CPMP) (2001). Points to consider on switching between superiority and non-inferiority. British Journal of Clinical Pharmacology, 52(3), 223–228.

D'Agostino, R. B., Massaro, J. M., & Sullivan, L. M. (2003). Non-inferiority trials: design concepts and issues - the encounters of academic consultants in statistics. Statistics in Medicine, 22(2), 169–86. http://doi.org/10.1002/sim.1425

Del Re, A. C. (2015). A Practical Tutorial on Conducting Meta-Analysis in R. The Quantitative Methods for Psychology, 11 (1), 37-50.

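### Test order is randomised by Latin square, but the primary paired t-test ignores test position: a modest loss of power, not a validity flaw while sequences are balanced

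*Protocol*

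**What the plan says.** SRT is measured in a single lab test at Visit 6 under three conditions: unaided, RMD (control, C) and IMD (test, T). Protocol 11.4.2 gives the reason for varying the order: "Test condition order will be randomized using a Latin square design to control any potential order effect". Section 7.3 says the same of lab tests in general: "The test condition order will be randomized using a latin square design".

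The analysis does not carry this through. Protocol 11.4 and SAP 3.2 describe a paired t-test of C-T and list its assumptions. In the SAP's words, "The non-inferiority test compares the difference to a non-zero quantity -M". Neither document mentions position, period or sequence in the model. The only covariate named is degree of hearing loss, post hoc (11.4.3). The CRF field list in 12.1.1 has the OLSA result but no field for the position at which each condition was tested.

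On size, Protocol 11.2 states: "For 90% power at the 0.025 significance level, the required sample size is about 24 subjects". The synopsis plans about 35 participants. Section 11.5 restricts the analysis to complete cases and does not replace drop-outs.

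**The concern.** A Latin square balances position over conditions, so position does not bias the mean of C-T. It does not take the position effect out of each subject's own difference. A subject tested on the RMD first and the IMD second carries one step of learning in C-T; a subject tested on the IMD first and the RMD last carries two steps the other way. A t-test on the raw differences treats this known, designed variation as noise. The interval for C-T is then wider than it need be, and the chance of showing non-inferiority is lower.

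The position of every test is known by design, so the variation can be removed at almost no cost. A position term would also protect the estimate if the sequences among analysed subjects turn out unequal.

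**Working it through.** **Inputs.** SAP section 4 uses "non-inferiority margin: 1.34, standard deviation: 2 dB, alpha: 0.025, beta: 0.1"; SAP 3.1 says "The non-inferiority margin for the trial will be set to 1.3 dB". The test is one-sided (Protocol 11.2). The 2 dB SD is that of the unaided-aided difference in the 2016 internal reference test (SAP 2.1), used as a stand-in for the SD of C-T. **L, the SRT gain per test position, is an assumption**: range 0 to 1 dB.

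**1. The plan's own figure.** n = [SD × (z₀.₉₇₅ + z₀.₉₀) / δ]², with z sum 1.960 + 1.282 = 3.242.
- δ = 1.345 (2 − 1.31/2, unrounded): 23.2, so 24. The plan's 24 is reproduced.
- δ = 1.3: 24.9, so 25.
- One-sided 0.05 with δ = 1.3 gives 20.3, so 21. The synopsis figure of 0.05 therefore fits 24 only if read as two-sided.

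With the t distribution, n=24, δ=1.3 and a true difference of 0, power is 86%. That is the baseline below.

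**2. Variance added by position.** Take the cyclic square unaided-RMD-IMD, RMD-IMD-unaided, IMD-unaided-RMD. Lower SRT is better, so a gain of L per later position contributes +L, +L and −2L to C-T.
- Mean: (1 + 1 − 2)L/3 = 0.
- Variance: (1 + 1 + 4)L²/3 = 2L². Using all six orders also gives 12L²/6 = 2L².
- SD of C-T: √(4 + 2L²) = 2.12 at L=0.5 and 2.45 at L=1.0.
- Normal-approximation n for 90% power at δ=1.3: 25 at L=0, 28 at L=0.5, 38 at L=1.0.

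**3. Power by simulation** (residual SD 2 dB, δ=1.3, one-sided 0.025, true difference 0). Adjusted means C-T regressed on two position contrasts, with n−3 degrees of freedom.

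| L (dB) | n=24 plain | n=24 adjusted | n=35 plain | n=35 adjusted |
|---|---|---|---|---|
| 0 | 86% | 86% | 96% | 96% |
| 0.25 | about 86% | 86% | 96% | 96% |
| 0.5 | 83% | 86% | 95-96% | 96% |
| 1.0 | about 74% | 86% | 92-93% | 96% |

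At L=0.25 and n=24 the loss is under one point. If learning occurs only after the first test, a 1 dB gain gives 82% vs 86% at n=24.

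**4. One-sided error at the margin, n=24, 8 per sequence.** Plain t-test: 2.5% at L=0, about 1.9% at L=0.5, 0.8-0.9% at L=1.0. Adjusted: about 2.5% throughout.

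**5. Unbalanced sequences.** With 9/9/6 analysed and the short group in the −2L sequence, C-T shifts by (9 + 9 − 2×6)L/24 = 0.25L towards the IMD. One-sided error of the plain t-test rises to about 4% at L=0.5 to 1.0; the adjusted analysis stays near 2.5%. With the short group in another sequence the shift is (6 + 9 − 2×9)L/24 = −0.125L. With 12/12/11 out of 35 it is (12 + 12 − 2×11)L/35 = 0.06L.

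**6. If the 2 dB already contains order variance.** At L=0.5 the residual SD is √(4 − 0.5) = 1.87. Plain power at n=24 stays at the baseline 86%, and adjustment raises it to 90%.

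**7. A three-condition model with pooled error.** An SD of 2 dB for C-T corresponds to a residual SD of 2/√2 = 1.41 per aided condition. Pooling averages the three variances. If the unaided residual SD is 2.24 (assumed), the pooled variance is (5 + 2 + 2)/3 = 3 instead of 2, and simulated power at L=0 falls to 76%. If it is 1.0, the pooled variance is (1 + 2 + 2)/3 = 1.67, and one-sided error rises to about 3.8%.

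**The case against.** The strongest reply is that the Latin square is the plan's control for order, that it works, and that the remaining loss is small.
- L is nowhere in the documents. L=1.0 means 2 dB between first and third test, as large as the whole amplification benefit that SAP 2.2 reports.
- Section 11.4.2 foresees training before the test, subjects do the OLSA at Visit 2 (9.3.2), and all took part in the earlier RMD testing (3.1). Each should reduce L.
- Enrolment is about 35, not 24. If nearly all complete, plain power stays above 90% at every L in the table.
- The planning SD comes from the same test setup (SAP 2.1) and may already contain order variance.
- The schedule marks lab-order randomisation in the same columns as the speech tests. If order is assigned there, earlier drop-outs cannot unbalance it.

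All of this stands, and it limits the size of the point. It does not supply the missing term, and the cost of adding it is negligible. The imbalance argument is only partly answered: 35 is not a multiple of 3, and removal of doubtful data (11.5) or of subjects with too little wear time (8.4) can follow order assignment.

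Two stronger readings are tempting. A reader might infer that ignoring position makes false non-inferiority more likely. Under balance the documents do not support that: the error rate falls below 2.5%. A reader might also take 9/9/6 as a prediction of bias. It is a worst-case illustration; the documents give no completion by sequence.

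**Conclusion.** The omission is real and the direction of its effect is clear: under balance, unbiased but less precise than the design allows. At the stated n of 24 the loss is under one point of power at L=0.25, about 3 points at L=0.5 and about 12 at L=1.0. At about 35 completers it is at most about 4 points over that range. These figures rest on an assumed L, a linear position effect and a residual SD of 2 dB taken from a different contrast. If that SD already includes order variance, the shortfall against planned power shrinks or disappears, though adjustment would still gain precision. Error above 2.5% arises only if the analysed sequences are unbalanced in the unfavourable direction. This is a modest efficiency gain worth taking, not a reason to doubt the validity of the planned test.

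**What to change.** In Protocol 11.4.2 and SAP 3.2, prespecify the primary analysis as the within-subject difference C-T regressed on the RMD-IMD position contrasts. For positions 2 and 3, each contrast is the indicator that the RMD was tested there minus the indicator that the IMD was. Leave the contrasts uncentred, so that the intercept is C-T at equal position. Compare the lower two-sided 95% limit of that adjusted mean difference with minus the margin. Keep the plain paired t-test as a sensitivity analysis.

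Do not replace it with a three-condition model with pooled residual variance. Noise in the unaided condition would then set the RMD-IMD interval, with loss of power or excess error as in step 7.

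Add the test position of each condition to the CRF. State this before the data are seen, since 11.4.6 requires later deviations to be justified.

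Cost: one CRF field, a few sentences, and two degrees of freedom (23 to 21 at n=24), or one if a linear position effect is assumed. That is under half a point of power if there is no order effect. No extra subjects or tests are needed.
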